13 TREATMENT DISCONTINUATION AND PREMATURE STUDY DISCONTINUATION

13.1 Protocol Treatment Discontinuation

13.1.1 Criteria for Discontinuing Protocol Treatment

Study drug discontinuation

Study drug interruption refers to a patient stopping either study drug during the course of the study, but then re-starting it at a later time in the study. If the study drug everolimus/ribociclib is interrupted for more than 4 weeks, the patient will be permanently discontinued from the study.

If the administration of study drug must be interrupted because of an unacceptable toxicity, dosing will be interrupted or modified according to rules described in TABLE 14, TABLE 15, TABLE 16, TABLE 17 for everolimus-cohort and TABLE 19, TABLE 20, TABLE 21, TABLE 22 and TABLE 23 for ribociclib-cohort. A patient who requires dose interruption (regardless of the reason for the interruption) lasting > 4 weeks (counting from the first day when a dose was missed) must discontinue study treatment. All study drug interruptions must be recorded on the appropriate Dosage Administration CRF.

Patients whose treatment is interrupted due to an adverse event or abnormal laboratory value must be followed at least once a week for 4 weeks and subsequently at 4 weeks intervals, until resolution or stabilization of the event, whichever comes first.

Study discontinuation refers to a patient's withdrawal from study drug. The reason for discontinuation from treatment must be recorded on the End of treatment CRF.

Patients who discontinue study drug > 4 weeks should be scheduled for an End of treatment Visit, as soon as possible, after discontinuing study drug, at which time all of the assessments listed for the End of treatment Visit will be performed. The complete End of treatment CRF documentation should be done within one week. The date and reason for stopping the study treatment should be recorded on the CRF.

Study drug will be discontinued for any of the following reasons:

- Tumor progression (as defined in section 10.2.)
- Toxicity/ Unacceptable adverse events
- Consent withdrawal/ Request by the patient
- Dose interruption of > 4 weeks
- Intercurrent illness that prevent further administration of study drug
- Need for any other types of anticancer therapy, except for palliative radiotherapy for bone lesions
- General or specific changes in the patient's condition which render the patient unacceptable for further treatment at the discretion of the investigator
- Pregnancy (applicable for eribulin cohort only)

If study drug is permanently discontinued, the patient will be considered to have completed study treatment. **All patients must have safety evaluations for 28 days after the last dose** of study drug.

Once the last dose of study drug is taken, no further AEs/SAEs will be collected on this protocol beyond the 28 day follow-up safety interval. After the last patient in the trial has taken the last dose of study drug, the current progression and survival status for all patients will be updated finally and recorded in the CRF.

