- Blood sampling for hematology and biochemistry (APPENDIX II)
- Blood sampling with Analysis Kit in week 3-4 and 9-12 only in patients who have given informed consent - part 3 for translational medical investigations (TraFo-Project)
- Blood sampling with Analysis Kit afterwards every 3 months in everolimus/ribociclib cohort only nse
- Tumor evaluation every 12 weeks (in the everolimus/ribociclib cohort together with blood sampling for CTC count)
- Quality of life assessment: EORTC QLQ-C30 and EORTC QLQ-BR23
- Tablet count, additional dispense of everolimus/ribociclib if necessary
- Pregnancy test (eribulin cohort only)
- Survival

Conclusion Visit of the Treatment Period

As soon as possible after disease progression, completion or premature discontinuation of protocol treatment or respectively 12 months after inclusion:

- Vital signs
- Physical examination
- Standard 12-lead ECG
- Adverse events
- Concomitant medication
- Documentation of end of protocol treatment and planned therapy after end of protocol treatment
- Blood sampling for hematology and biochemistry
- Blood sampling with Analysis Kit
- Quality of life assessment: EORTC QLQ-C30 and EORTC QLQ-BR23
- Tablet count, collection of unused everolimus/ribociclib
- Pregnancy test (eribulin cohort only)
- Survival
- Reminding patient of the follow-up procedures planned

Follow up assessments

Between 2 and 4 weeks after Conclusion Visit of the Randomized Treatment Period and then every 3 months:

- Adverse events which are \geq grade 3 NCI CTCAE and/or serious
- Concomitant medication
- Survival

Objectives and Endpoints of Clinical Trial

Primary objective:

Everolimus/Ribociclib cohort (DIVa)

The primary objective is to investigate the clinical efficacy of everolimus/ribociclib (as assessed by the CTC clearance rate) in combination with endocrine therapy in postmenopausal patients with hormone-receptor positive, HER2-negative metastatic breast cancer and persisting only HER2-negative circulating tumor cells (CTCs).

Eribulin cohort (DIVb)

The primary objective is to investigate the clinical efficacy of eribulin (as assessed by progression-free survival, PFS) both in patients with HER2-negative, hormone-receptor positive metastatic breast cancer and indication to chemotherapy and triple-negative metastatic breast cancer both with persisting only HER2-negative CTCs.

Secondary objectives:

In General

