4.3 Schedule

The individual study participation begins with the screening visit, consists of endocrine therapy plus everolimus/ribociclib or therapy with eribulin (depending on the treatment cohort) and ends with disease progression, the patient's death or with completion of the follow-up period. The estimated maximum duration of individual study participation is 36 months and 3 weeks both for the everolimus/ribociclib cohort and the eribulin cohort.

Patient participation is divided in 3 consecutive periods:

Pre-Treatment Evaluation Period:

Content:	Examinations and collection of data relevant to decide on patients' eligibility for further study participation. Informed consent 1
Period:	From screening to inclusion
Maximum duration:	3 weeks
Visits:	From Screening Visit to end of Inclusion Visit

Treatment Period:

Content:	Endocrine therapy combined with everolimus/ribociclib or chemotherapy with eribulin.
----------	--

Assessment of efficacy and safety data.
Informed consent 2 and 3

Period: From inclusion until disease progression or occurrence of other criteria for treatment discontinuation

Maximum duration: 12 months* (both for the everolimus/ribociclib cohort and the eribulin cohort) or until progress / death or discontinuation due to toxicities or other reasons

Visits: From Inclusion Visit to Conclusion Visit (4 weeks after last application of everolimus/eribulin)

*After treatment period the treatment with everolimus/ribociclib or eribulin can be extended if medically indicated. Patients will be followed up for toxicity and efficacy in such cases. The drug will be supplied by Novartis (everolimus/ribociclib), respectively Eisai (eribulin) on study terms for the duration of the individual study participation (including 2-year-period of follow-up assessments).

Follow-Up period:

[figure not shown]
Content: Assessment of survival, adverse events and concomitant medication. Treatment of the metastatic disease at the investigator's discretion

Period: From end of study treatment until the patient has either died or completed the 24-months follow-up period

Maximum duration: 24 months (estimation)

Visits: From Conclusion Visit of the Treatment Period to the last Follow-Up Visit

Figure 9: Clinical Trial Design

Entire Study:

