8.4.2 Dose Adjustments

In General

Doses may be held or reduced for hematologic and other adverse events (see section 8.3.2.1). Dose adjustments are to be made according to the system showing the greatest degree of toxicity. Once dose is reduced due to adverse events, patients should not be re-challenged to a higher dose level.

Dose reductions and delays of treatment should follow general GCP criteria for the application of antineoplastic drugs (Repetto et al. 2003, NCCN-Guidelines) and should be made according to the SPC and/or investigator's brochure. The latest versions of the SPCs ("Fachinformation" according to German Drug Law) of the standard therapy will be provided on the DETECT IV website or by contact the DETECT Study Office in Ulm (Univeritäts-frauenklinik Ulm, Studienzentrale, [name], [name], [contact], [contact], Email: [contact]).

The antineoplastic treatment of a patient can be postponed for up to 4 weeks to allow resolution of toxicity. The investigator must consult the DETECT IV Study Office prior continuing therapy for any patient requiring a delay of study treatment of more than two weeks for any reason.

All patients who require permanent discontinuation of eribulin will be withdrawn from the treatment intervention schedule (start of the 2-year follow-up period).

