9.2 Evaluation during Follow-Up Period (after Treatment Period)

Follow-up procedures are study specific and not part of the usual routine in case of metastasizing breast cancer.

Between two and four weeks after conclusion visit of the treatment period and then at least every three months the following is assessed during routine visits in the clinical trial center or via telephone call:

- Adverse events which are \geq grade 3 NCI CTCAE and/or serious
- Concomitant medication
- Survival

Therapy during Follow-Up Period is as described in section 12.1.3 “Therapy after end of protocol treatment”.

10 **CRITERIA FOR MEASUREMENT OF STUDY ENDPOINTS**

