11 ADVERSE EVENT REPORTING

11.1 Definitions, Collection and Recording of Adverse Events by the Investigator

An adverse event (AE) is any untoward medical occurrence in a patient administered a pharmaceutical product and which does not necessarily have a causal relationship with this treatment. An adverse event (AE) can therefore be any unfavorable and unintended sign (including an abnormal laboratory finding), symptom, or disease temporally associated with the use of a medicinal (investigational) product, whether or not related to the medicinal (investigational) product. In particular this includes new findings or changes from baseline in laboratory test results or any other safety assessments (e.g. ECGs, radiological scans, vital signs assessments) felt to be clinically significant in the medical and scientific judgment of the investigator.

During treatment period AEs are collected by the investigator at least on every visit of the patient at the study site, whether it is a scheduled study visit or not.

During the follow-up period (after conclusion of the treatment period) only adverse events are collected by the investigator which are \geq grade 3 NCI CTCAE and/or serious.

Every adverse event is followed up until it has subsided or stabilized.

On each AE the following data are raised and documented by the investigator in the respective electronic case report form:

- Diagnosis or each single symptom if diagnosis is not available,
- Date and time of onset and end of AE,
- Whether onset was after the first administration of study medication (yes/no),
- Course (continuous / intermittent, if intermittent: number of episodes),
- Whether the AE is a reportable serious adverse event (serious/ non-serious, for the definition of "reportable serious event" cf. section 1.3),
- Intensity (grade 1 to 5 according to the NCI Common Terminology Criteria for Adverse events (CTCAE) version 4.03),
- Causal relationship with investigational medicinal product (no (not related) / yes (reasonable possibility)),
- Counter-measures (none/ dose reduced/ drug withdrawn/ other drug treatment/ other measures),
- Outcome (recovered/ recovering/ not recovered/ recovered with sequelae/ fatal/ unknown),

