APPENDIX II – PATIENT EVALUATION FLOW SHEET

Visits	Screening Visit	Inclusion Visit	Control Visits	Conclusion Visit of Treatment Period	Follow-up Assessments
Time	≤ 21 days prior to end of Inclusion Visit	≤ 21 days after Screening Visit	Every 3 to 4 weeks (Everolimus/ribociclib cohort) and every 6 weeks (eribulin cohort)	12 months after first dose or at premature termination of protocol treatment	2 to 4 weeks after Conclusion Visit, then q 3 months
Periods	Pre-Treatment Evaluation Period		Treatment Period		Follow-Up Period
Informed consent - part 1 in blood sampling for CTC count and HER2 status on CTC ¹	X				
Informed consent - part 2 in study participation ¹		X			
Informed consent - part 3 in blood sampling for translational medical investigations ^{1,2}		X			
Allocation of the patient identification number	X				
Demography (YOB)*	X				
Date of primary tumor diagnosis*	X				
Information on primary breast cancer (TNM*, histology*, grading*, localisation**, surgery**)	X				
Information on metastases (date of diagnosis*, localization*, surgery**)	X				
HER2 status on primary tumor tissue and/or biopsies from metastatic sites	X				
Hormone receptor status on primary tumor tissue and/or biopsies from metastatic sites ⁴	X				
Adjuvant/Neoadjuvant Therapy**	X				
Number of prior chemotherapy lines for metastatic disease*, type of therapies for metastatic disease**	X				
Blood sampling for CTC within the clinical trial	X ⁵ Screening Kit		X ¹⁷ (every 12 weeks) with Analysis Kit everolimus/ribociclib cohort only	X ¹⁷ (Analysis Kit)	
Blood sampling for translational medical investigations	X ⁶ (part of Screening Kit)	X ¹⁹ Analysis Kit	X ¹⁹ (Analysis Kit) Only at visits week 3-4 and 9-12		
Patient height + weight		X			
Medical/surgical history		X			
Concomitant diseases		X			
Ongoing toxicities attributed to prior anti-cancer therapies ³		X			
Prior anticancer medication, other relevant prior medication		X			
Concomitant medication		X	X	X	X

Visits	Screening Visit	Inclusion Visit	Control Visits	Conclusion Visit of Treatment Period	Follow-up Assessments
Documentation of and check for compatibility of planned endocrine therapy in combination with everolimus		X			
Protocol treatment		X	X	X ¹⁶	
Vital signs (heart rate, blood pressure, temperature)		X	X	X	
Physical examination		X	X	X	
Adverse Events		X	X	X	X
Hematology ⁷		X ^{9, 20}	X ^{20, 21}	X	
Biochemistry ⁸		X ⁹	X ²⁰	X	
Pregnancy test (eribulin cohort only)		X ⁹	X	X	

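### Section 13.1.1 stops all AE/SAE collection 28 days after the last dose, while the follow-up schedule requires AE collection about every three months for up to 24 months; for patients off drug a site cannot obey both

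*Protocol*

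**What the plan says.** Section 13.1.1, after listing the reasons for stopping study drug and requiring safety evaluations for 28 days after the last dose, adds that "no further AEs/SAEs will be collected on this protocol beyond the 28 day follow-up safety interval". It names SAEs as well as AEs and makes no exception for severity.

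Other current sections give the opposite instruction:

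- Section 9.2 sets a contact two to four weeks after the Conclusion Visit, "and then at least every three months the following is assessed during routine visits in the clinical trial center or via telephone call". The first item on its list is adverse events of grade 3 or higher and/or serious.
- The synopsis, under follow-up assessments, has the same item with the timing "Between 2 and 4 weeks after Conclusion Visit of the Randomized Treatment Period and then every 3 months".
- Appendix II marks adverse events in the follow-up column, timed "2 to 4 weeks after Conclusion Visit, then q 3 months".
- Section 4.3 gives the follow-up content as "Assessment of survival, adverse events and concomitant medication" and its period as "From end of study treatment until the patient has either died or completed the 24-months follow-up period".
- Section 11.1 sets the severity filter: "During the follow-up period (after conclusion of the treatment period) only adverse events are collected by the investigator which are" grade 3 or higher and/or serious.

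Entry into follow-up after stopping treatment is stated by cohort. For eribulin, section 8.4.2 says "All patients who require permanent discontinuation of eribulin will be withdrawn from the treatment intervention schedule (start of the 2-year follow-up period"). For the everolimus and ribociclib patients, sections 8.2.2 and 8.3.2 require permanent discontinuation of both the investigational drug and the endocrine agent.

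**The concern.** Within one protocol, one sentence forbids what the assessment schedule requires. A non-serious grade 3 event that starts on day 60 after the last dose is recorded at a site that works from section 9.2 or the flow sheet, and omitted at a site that works from section 13.1.1. Up to 100 centers are planned, so late event counts would depend partly on which section each site read.

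Safety is a secondary endpoint assessed mainly by adverse event frequency (section 1.2.2 and the synopsis; section 15.4 repeats the method). The conflict concerns what sites collect. An analysis plan can decide how to tabulate late events, but it cannot recover events that were never entered.

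**Working it through.** The plan states no figure to reproduce. The check compares the texts and then does simple calendar arithmetic.

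**Step 1. Do the rules apply to the same patients?** Follow-up runs from the end of study treatment to death or month 24 (section 4.3). It therefore includes an eribulin patient who has stopped permanently (8.4.2), and an everolimus or ribociclib patient who has stopped both agents (8.2.2, 8.3.2). Section 13.1.1 addresses the same patients, since its clock starts at the last dose.

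**Step 2. Can drug continuation reconcile them?** Section 4.3 lets study drug be extended into follow-up if medically indicated. In such a patient the last dose comes later and both rules can be obeyed while drug continues. But extension is optional, and its footnote adds toxicity follow-up for those patients without restricting section 9.2 to them. Patients off drug remain in conflict.

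**Step 3. Window lengths.** Inputs: 28 days (13.1.1) and 24 months (4.3, synopsis), with 30.44 days per month.

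- 24 × 30.44 = 730.6 days
- 28 / 730.6 = 3.8%
- 730.6 − 28 = 702.6 days required by the schedule and barred by 13.1.1, at most

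**Step 4. Contacts affected.** Three-monthly contacts up to month 24 number 8 if counted from the Conclusion Visit (months 3, 6, …, 24). They number 7 if counted from a first contact at 0.5 to 1 month (months 3.5–4, …, 21.5–22). The timing of the Conclusion Visit itself varies: section 9.1 wants it as soon as possible after progression or discontinuation, while section 4.3 places it 4 weeks after the last application.

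| Conclusion Visit | First contact, days after last dose | Contacts beyond day 28 |
|---|---|---|
| At the last dose | 14–28 (inside) | 7–8 |
| 4 weeks after it | 28 + 14 = 42 to 28 + 28 = 56 (outside) | 8–9 |

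Only the adverse event item conflicts. Survival and concomitant medication are collected at these contacts under either reading.

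**Step 5. Ceiling on patients.** Section 15.3 plans 90 + 90 + 120 = 300 patients. Each counts only while alive, in follow-up and off drug, so 300 is an upper bound.

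**Step 6. What is protected elsewhere?** Section 11.2 requires all SAEs to be reported within 24 hours and sets no end date, and section 11.4 lists post-study SUSARs as reportable. Grade 3+ and serious events up to day 28 are captured under either rule. Non-serious grade 3+ events that start after day 28 are protected only by the follow-up schedule that 13.1.1 contradicts.

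**The case against.** Several points on the other side have weight.

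- Section 8.6.2 also gives 28 days of safety follow-up after the last dose, so 13.1.1 is not alone. This stands in part: 8.6.2 leans to the 28-day side, but it does not bar later collection and can coexist with section 9.2. The documents do not show which window the sponsor meant. The fix below follows the longer one because it is the one built into the visit schedule.
- Section 11.1 is a severity filter with no stated duration and could be read together with a 28-day limit. This stands. The hard conflict comes from the three-monthly schedule in section 9.2, the synopsis and Appendix II.
- The opening of section 4.3 says that participation ends with progression, death or completed follow-up, which might suggest that patients who progress are not followed. The synopsis ends participation only at death or completed follow-up, and section 4.3 itself defines the follow-up period that way. The sentence does not remove the conflict.
- A reader might infer that every patient who stops everolimus or ribociclib is caught. Sections 8.2.2 and 8.3.2 do not support that: a patient who keeps the endocrine agent is not moved into follow-up by those sections.
- A reader might also infer that late SAEs are lost, or that the safety results as a whole are unreliable. Sections 11.2 and 11.4 partly protect late SAEs, and section 11.1 has every adverse event followed until it subsides or stabilizes. Therapy in follow-up is at the investigator's discretion (13.1.3), so late counts in this uncontrolled study are descriptive in any case.

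**Conclusion.** The contradiction is real and stands in current text. For patients off drug, 13.1.1 bars adverse event collection that the follow-up schedule requires, for up to about 703 days and at 7 to 9 contacts per patient. These figures compare calendar windows; they do not measure lost safety information. No event rate is given or assumed, so the number of missed events cannot be stated.

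The exposure is mainly non-serious grade 3+ events starting after day 28. The primary endpoints (CTC clearance rate and PFS) and the grade 3+/serious counts to day 28 do not change. The point is minor: worth correcting at the next amendment, and no reason to doubt the main results. It rests on two readings: that section 9.2 covers all patients in follow-up, as it is written, and that follow-up begins when study treatment ends, as section 4.3 states.

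**What to change.** Replace the 13.1.1 sentence with: 'For patients who stop study drug during or at the end of the treatment period, all AEs are collected until 28 days after the last dose of study drug; thereafter, to the end of the 24-month follow-up, AEs of grade 3 or higher and/or serious AEs are collected at each follow-up assessment (sections 9.2 and 11.1).' The all-AE part adds no visit, because the synopsis and sections 8.2.1.9 and 8.3.1.9 already require a visit 4 weeks after the last dose to report any adverse events.

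That sentence alone would leave a clash. Section 9.1 can place the Conclusion Visit right after discontinuation, so follow-up may begin before day 28, and 11.1 then admits only grade 3+ and/or serious events. In 11.1 and 9.2, and in the matching synopsis lines, let the severity limit start at the later of the Conclusion Visit and day 28 after the last dose for patients who have stopped study drug. Patients who continue study drug in follow-up stay under the grade 3+/serious rule.

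Add a cross-reference in 8.6.2 that its 28 days are the all-AE window. Report events up to 28 days after the last dose separately from later ones.

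The cost is a few lines of amendment text and no new visits, since adverse events are already scheduled at every follow-up assessment.

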13.1.2 Duration of Protocol Treatment

Duration of endocrine therapy:

- Depends on the occurrence of tumor progression or other criteria for discontinuation (see section 12.1.1.)
- The treatment can be extended in case of missing progress. Conclusion Visit should be performed 12 month after recruitment (End of treatment period under study conditions) or as soon as possible if criteria for discontinuation occur.

Duration of treatment with everolimus/ribociclib:

- Depends on the occurrence of tumor progression or other criteria for discontinuation (see section 12.1.1.)
- The treatment with everolimus/ribociclib can be extended if medically indicated. Conclusion Visit should be performed 12 month after recruitment even if therapy with everolimus is continued or as soon as possible if criteria for discontinuation occur.

Duration of treatment with eribulin:

- Depends on the occurrence of tumor progression or other criteria for discontinuation (see section 12.1.1.)
- The treatment with eribulin can be extended if medically indicated. Conclusion Visit should be performed 12 month after recruitment even if therapy with eribulin is continued or as soon as possible if criteria for discontinuation occur.

